#### *b. Study Visits and Procedures*

A stent with reference notches made by #1/2 bur at a 2 mm distance from the gingival margin at the mesio-buccal, mid-buccal and disto-buccal sites will be fabricated. The stent will be made based on the patient's dental model to have the best fit. A new stent with the same design will be made after patients have permanent restorations and the stent will be used to measure the parameter at the 12-month follow-up

The following measurements will be carried out at the visits:

- 1) Soft tissue distance from each of the three notches (mesio-buccally, mid-buccally and disto-buccally, respectively): the distance is measured from the notch to the gingival margin at three sites; it is measured at implant placement visit (baseline), 3 months, 6 months, and 12 months.
- 2) Horizontal defect dimension (HDD) defined as horizontal distance from the implant shoulder to the buccal alveolar socket wall, measured in the mid-buccal site; it is measured only at implant placement visit (the first visit).
- 3) Vertical defect dimension (VDD) defined as vertical distance from implant shoulder to the apical contact with the socket wall, measured in the mid-buccal site; it is measured only at implant placement visit (the first visit).
- 4) Buccal soft tissue thickness will be measured following the extraction using the endodontic file and the digital caliper (one measurement/ mid-buccal/6mm apical to gingival margin); it is measured before and after implant surgery at the first visit, 6 months and 12 months.
- 5) Probing depth (PD): probing depth is defined as the distance from the gingival margin to the tip point of the probe (Williams probe). PDs will be measured at 6 sites per tooth (mesio-buccal, mid-buccal, disto-buccal, disto-palatal, mid-palatal, mesio-palatal); it is measured before surgery at the first visit, 3 months, 6 months and 12 months.
- 6) Bleeding on probing (BOP): the prevalence of bleeding on probing at six sites (mesio-buccal, mid-buccal, disto-buccal, disto-palatal, mid-palatal, mesio-palatal) of the tooth/implant will be documented at the first visit, 3 months, 6 months and 12 months.
- 7) Plaque index (PI): A periodontal probe will be swept along each site to all the teeth to identify the presence or absence of plaque accumulation at the first visit, 3 months, 6 months and 12 months. A dichotomous scoring system will be used with one (1) and zero (0) equaling presence and absence, respectively, of plaque.
- 8) Buccal-palatal dimension of the ridge at the site of implant placement: the dimension will be measured at different reference points (3 mm, 6 mm from the baseline gingival margin) on the study model. Impressions for study models will be taken at the first visit, at 3 months, 6 months and 12 months. The measurement will be done by the digital caliper and the computer assisted scanned images.
- 9) Buccal plate thickness: it will be measured on the images of dental cone beam computed tomography. The patients will have the images taken with a stent before the surgery and 6 months after the surgery. The stent will be made based on the patient's dental model. The midline of the implant site will be buccally and palatally marked with gutta percha.
- 10) Interproximal bone level: a film holder with silicon putty to aid in reproducibility of the radiograph position will be used. The mesial and distal crestal bone level will be measured using the MIPACS software. Implant platform will serve as the reference point. Vertical and horizontal changes (depth and width of the vertical defect on the mesial and/or distal aspect of the implant, if present) will also be measured from radiographs taken at the time of completion of surgery, at 6 and 12 months. Dose and frequency of x-rays in the study are standard of care for any implant patient in UTSD, PISH or in standard clinical practice, and are not altered for the purpose of the study. (Medical status is updated and recorded at each visit, including verification that female patients are not pregnant prior to x-ray taking; this is also standard of care).
- 11) The diameter of the apical radiolucency, when initially present, will be monitored radiographically. Any lesions present in the radiography will be assessed immediately after surgery and 6 months.
- 12) Blood flow of gingiva: The laser Doppler flowmeter is a noninvasive measure of capillary blood perfusion. The readings are obtained by placing the tip on the

surface of buccal gingival. It is measured before and after implant surgery at the first visit, 3 months, 6 months and 12 months.

*c. Final Study Visit:*

The 12-month follow-up will be the subject's last visit for this clinical trial. The patients will have clinical measurements (PD, BOP, PI), dental impressions taken, and periapical radiographic examination. All subjects will have periodontal maintenance in the periodontics clinic of UTSD or PISH in the future.

*d. Post Study Follow up and Procedures*

The subjects will continue having routine maintenance appointments to follow up the health and function of implants and teeth in the periodontics clinic of UTSD or PISH. If the patients have symptoms of inflammation and signs of progression bone loss, the necessary treatments, such as debridement, will be performed.

*e. Discontinuation Visit and Procedures*

Subjects are free to withdraw from participation in the study at any time upon request. A subject may be discontinued from participation in the study for any of the following reasons:

1. Withdrawal of consent
2. Subject noncompliance with the protocol, as determined by the investigator
3. Any event or condition that would make continued participation in the study not in the best interest of the subject, as determined by the investigator
4. Pregnancy
5. Development of any medical condition that might affect the treatment and clinical outcomes, as determined by the investigator.
6. Initiation of any treatment or exposure that might affect the outcomes of implant therapy, as determined by the investigator.
7. Investigator discretion

Any subject with a serious adverse event, such as life-threatening diseases, hospitalization, that is ongoing at the time of discontinuation will be followed until the event returns to baseline, resolves, or stabilizes. If the serious adverse event does not meet these outcomes within 30 days after discontinuation or after study completion, the subject will be referred to an appropriate practitioner for continued care. If the study is discontinued, subjects will be referred back to the qualified clinicians for necessary dental care.

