## STUDY PROTOCOL

### 1. BACKGROUND AND RATIONALE

#### 1.1. General Introduction

The concept of immediate implant was proposed about forty years ago (Schulte and Heimke 1976; Schulte et al. 1978). Over the past few decades, several clinical trials had demonstrated immediate implantation has high survival rate and stable interproximal bone levels (Becker et al. 1998; Chen et al. 2007; Lazzara 1989; Sanz et al. 2014; Schropp et al. 2003), similar to conventional delayed implant placement. Compared to delayed placement, immediate implantation is able to reduce the number of clinical visits and surgical procedures, by this diminishing patient morbidity, and in some cases, enabling immediate restoration (Lang et al. 2012). In addition to these advantages, it has been suggested that immediate implant preserves alveolar bone dimensions (Denissen et al. 1993; Lazzara 1989; Paolantonio et al. 2001; Watzek et al. 1995). However, several experimental studies and clinical trials demonstrated significant changes of bony ridge dimensions in the surgical site of immediate implantation (Botticelli et al. 2004; Botticelli et al. 2006).

Generally, the dimensional change of buccal site is greater than that of the lingual/palatal site (Botticelli et al. 2004; Brownfield and Weltman 2012; Lee et al. 2014). The buccal bone (Lee et al. 2014) or buccal ridge dimensional alteration (Grunder 2011; van Kesteren et al. 2010) following immediate implant placement without placing any bone graft or tissue graft is about 1 to 1.5 mm within one year follow-up. The change of bone/ridge dimension also accompanies with gingival recession. The mean mid-buccal gingival recession is approximately 0.5 to 1mm within one year follow-up following immediate implantation and advanced mid-buccal gingival recession (>1 mm) sometimes happens (Cosyn et al. 2012). Many clinicians try to prevent the changes of soft tissue and hard tissue in the esthetic demanding sites by using different methods. The effect of placing bone grafts and/or immediate temporization has been proved on compensating soft tissue and hard tissue collapse (Cosyn et al. 2012; Tarnow et al. 2014). However, the use of autogenous tissue graft or alternative graft, such as collagen matrix and acellular dermal matrix, combined with immediate implant is equivocal.

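### The 12-month gingival level is read from a second stent with no stated rule for carrying over the baseline notch height, so earlier recession may drop out of the 12-month change

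*Combined protocol and SAP*

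**What the plan says.** Section 6.3 b describes the first stent as "A stent with reference notches made by #1/2 bur at a 2 mm distance from the gingival margin", at three buccal sites. On construction it adds: "The stent will be made based on the patient's dental model to have the best fit". Item 1 of the same section defines gingival level: "the distance is measured from the notch to the gingival margin at three sites". Readings are due at implant placement and at 3, 6 and 12 months.

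The stent then changes: "A new stent with the same design will be made after patients have permanent restorations". This replacement, not the first stent, serves for the reading at 12 months. Section 6.3 a has the final impression taken at 6 months and the crown delivered no more than a month later, so the second stent dates from about 6 to 7 months at the earliest.

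The ridge measurement in item 8 is anchored differently. Its reference points are "3 mm, 6 mm from the baseline gingival margin". The stent notches carry no such tie to baseline.

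Change in gingival level is a secondary outcome in Sections 3.1 and 5.1, and it is also named under the primary objectives in Section 2.2. Section 11.2 c applies one-way ANOVA between groups and paired t-tests over time to primary and secondary outcomes alike.

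**The concern.** A notch-to-margin distance measures change only if the notch stays where it was. The one feature of the stent design that bears on the measurement is the distance from the notch to the margin. Repeating that design on a later model puts the notch 2 mm from a margin that may already have receded. The 12-month reading minus the baseline reading would then contain only the recession that followed the new stent.

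This would bias the 12-month result towards a stable margin in every arm, and a stable gingival level is one of the expectations in Section 2.1. It could also make recession look smaller at 12 months than at 6, and it could narrow a real difference between arms.

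The plan contains none of the usual safeguards: no transfer of the original notch height, no paired reading with both stents, no reading when the stent is changed, and no fixed landmark on a neighbouring tooth. It does not say which model the second stent is built on. Two clinics recruit, so operators could follow the text differently.

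**Working it through.** The plan gives no expected difference or precision for gingival level, so there is no figure of its own to reproduce. The sample-size statements in Sections 3.1 and 11.1 concern ridge dimension. The check is measurement arithmetic.

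**Inputs**
- Notch distance: 2 mm (Section 6.3 b).
- First-year recession R: 0.5 to 1 mm. Section 1.1 states: "The mean mid-buccal gingival recession is approximately 0.5 to 1mm within one year follow-up following immediate implantation".
- Share s of R that occurs before the new stent is made: not in the documents. It is an assumption, shown over its whole range from 0 to 1.

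**Formulas**
- Notch held at baseline height: 12-month reading = 2 + R, so the change is R.
- Notch re-cut 2 mm from the later margin: 12-month reading = 2 + R(1 − s), so the apparent change is R(1 − s) and the loss is R × s.

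| s | Apparent change, R = 0.5 | Loss | Apparent change, R = 1.0 | Loss |
|---|---|---|---|---|
| 0 | 0.50 mm | 0 | 1.0 mm | 0 |
| 0.5 | 0.25 mm | 0.25 mm | 0.5 mm | 0.5 mm |
| 0.8 | 0.10 mm | 0.40 mm | 0.2 mm | 0.8 mm |
| 1 | 0 | 0.50 mm | 0 | 1.0 mm |

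The loss therefore runs from 0 to 1 mm.

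**From 6 to 12 months.** If all recession before the new stent is present by 6 months, the apparent change is R(1 − s) − R × s = R(1 − 2s). At s = 0.8 this is −0.3 mm for R = 0.5 and −0.6 mm for R = 1.0, a false coronal gain.

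**Between arms.** Assume true 12-month recession of 1.0 mm in one arm and 0.5 mm in another, a difference of 0.5 mm. With the same s in both, the apparent difference is 0.5 × (1 − s): 0.25 mm at s = 0.5, 0.1 mm at s = 0.8 and 0 at s = 1. The proportional shrinkage needs that equality. With s = 0.8 and s = 0.5 respectively, the difference is 1.0 × 0.2 − 0.5 × 0.5 = 0.20 − 0.25 = −0.05 mm, and the order reverses.

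**Which model.** The only impression listed after the crown is the one at 12 months. A second stent built on that model with re-cut notches would read about 2 mm in every patient by construction, which is the s = 1 row.

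**With the reference held at baseline**, the 12-month reading is 2.5 mm (R = 0.5) to 3.0 mm (R = 1.0), and the full change is recovered whatever s is.

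**The case against.** The best defence is that a stent of the same design means one with its notches at their original height, remade only because the crown has changed the site. Baseline models exist, so this could be done, and then nothing is reset. That reading is possible, and a reader who infers that recession will certainly be zeroed goes further than the text. The text, however, does not state that intention or give a method for it, and it leaves out the baseline anchor that item 8 supplies for ridge width. The gap stands on either reading.

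The size is also open to challenge, fairly. Section 1.1 gives 0.5 to 1 mm for immediate implantation in general, and the same section credits bone grafting with compensating for tissue collapse. Section 6.3 a puts xenograft in the gap in every arm. Recession here may be smaller, and the documents give no figure for this regimen. A reader might also infer a minimum loss of 0.25 mm by supposing that at least half of the recession comes early. No figure in the documents supports that floor.

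The information is not necessarily lost to the trial. Models are planned at the first visit and at 3, 6 and 12 months, with scanned images. What stands is that the plan uses them for ridge width and not for gingival level.

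Finally, a reader might extend the point to soft tissue thickness, taken at "one measurement/ mid-buccal/6mm apical to gingival margin" without a baseline anchor. That does not follow. A site defined relative to the current margin is a defensible choice, and nothing in the documents shows a resulting error in thickness.

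**Conclusion.** The point holds as a gap in the measurement definition. The 12-month gingival level has no documented common reference with the baseline, 3-month and 6-month values, and the literal reading of Section 6.3 b removes recession that precedes the second stent. The loss is 0 to 1 mm per patient on average. That range rests on the general recession figure in Section 1.1, on an assumed early share of 0 to 100%, and on the notches being re-cut from the later margin. Differences between arms shrink in proportion only if the early share is similar across arms.

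The scope is narrow: one outcome, listed as secondary although also named under the primary objectives, at one visit. A reader might infer that the main result is at risk. It is not, because ridge dimension is measured on models from the baseline margin, and the 3- and 6-month gingival readings precede the second stent. Recession after the second stent is made is still captured, unless that stent is built on the 12-month model.

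**What to change.** State in Section 6.3 b that the notches of the second stent are transferred to their baseline height from the baseline model, using the adjacent teeth as the fixed reference, and name the model on which the stent is built. Section 3.3 requires adjacent teeth to be present, so the reference is available in every patient.

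Alternatively, compute the 12-month gingival level by superimposing scans of the baseline and 12-month models on the adjacent teeth. The impressions and scanned images are already in item 8. If this route is taken, reading the 3- and 6-month models in the same way would put all visits on one method.

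The cost is one or two sentences in the protocol and a small laboratory or analysis step. No extra visit or impression is needed for the scan route. The stent route needs no additional impression for the notch height, although the protocol should say which impression gives the fit over the crown.

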**b. Rationale for Materials Selected**

SCTG will be harvested from the palate and the required size depends on the size of the surgical site. Generally, the width of the tissue graft should be sufficient to cover the adjacent interproximal papillae, and the length could be standardized as 10 mm. The size of the tissue graft is able to cover the area usually having the most significant dimensional changes following extraction (Morimoto et al. 2015; Tarnow et al. 2014). The thickness of harvested tissue graft will be trimmed to the range from 1-1.5 mm (Hurzeler and Weng 1999).

The ADM is a commercial product and has multiple sizes available. One piece of 10mmx10mm ADM can be trimmed to an appropriate size defined by the criteria for SCTG. According to the manual instruction, the thickness of ADM ranges from 0.9-1.6mm which will be close to the thickness of SCTG utilized in this study.

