## **2. HYPOTHESIS AND OBJECTIVES**

### **2.1. Hypothesis**

The hypothesis is that ridge dimensional reductions in the sites of immediate implant combined with autogenous tissue graft/acelluar dermal matrix are significantly less than the sites of immediate implant alone. Soft tissue augmentation is able to increase gingival thickness and limit resorption of bone by expanding the dimension of peri-implant mucosa. In addition to limited changes of ridge dimension and increased gingival thickness, stable gingival level and increased width of keratinized gingiva could also be found following soft tissue augmentation.

Placement of acellular dermal matrix has comparable clinical outcomes to placement of autogenous tissue graft because the clinical trials of mucogingival surgery, such as root coverage, show acellular dermal matrix is as effective as autogenous tissue graft.

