At the first appointment, all clinical measurements will be performed (probing depth (PD), clinical attachment level (CAL), bleeding on probing (BOP), plaque index (PI)) and the impression of maxillary and mandibular dentition will be taken. One periapical radiography of the surgical site will be taken after the surgery is finished. After verification that the local anatomical inclusion criteria are met, patients will be randomized to one of three treatment groups. All implants will be placed according to standard protocol at a subcrestal position (1 mm below the buccal crest) engaging the palatal wall without elevation of a mucoperiosteal flap. The gap between the implant and alveolar bone will be filled with xenograft (Geistlich Bio-Oss®) and covered by collagen dressing (CollaTape®). In the groups having soft tissue augmentation, intrasulcular incisions will be carried out to partially dissect the buccal flap from mesial papilla to distal papilla. The SCTG or ADM will be inserted into the dissected buccal flap. The SCTG will be subepithelially harvested from the palate of the patient. The width of tissue graft will be equal to the distance between the interproximal papillae on the level of buccal gingival margin. The length of SCTG will be standardized as 10 mm. The thickness of SCTG will be standardized as 1-1.5mm. The size of ADM will be standardized following the same principle. The SCTG tissue graft or ADM will be stabilized by sling suture (chromic gut 5-0).

In the three groups, the straight healing abutment will be delivered immediately after implant placement provided that the implant shows primary stability and has engaged in the bone with an insertion torque of 25 Ncm or more (Norton 2004). In case of a lower insertion torque, the protocol will be abandoned, a cover screw will be placed, and a two stage implant protocol will be followed. All patients will receive a permanent restoration at 6 months after surgery, if the implant is deemed to be successful (Misch et al. 2008). The placement of xenografts aims to optimize the esthetic outcomes.

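### Buccal soft tissue thickness is read 6 mm from a gingival margin not fixed at baseline, so the reading point can move with recession; anchor it, including on the 12-month stent

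*Combined protocol and SAP*

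**What the plan says.** All references are to the combined protocol and SAP.

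- **Thickness site and timing (6.3 b, item 4).** There is a single reading per occasion, "one measurement/ mid-buccal/6mm apical to gingival margin". On timing, "it is measured before and after implant surgery at the first visit, 6 months and 12 months".
- **Ridge dimension site (6.3 b, item 8).** The levels on the study model are "3 mm, 6 mm from the baseline gingival margin", so this reference point is fixed.
- **Recession (1.1).** "The mean mid-buccal gingival recession is approximately 0.5 to 1mm within one year follow-up following immediate implantation". The section adds that recession above 1 mm sometimes occurs. It also says that bone grafting and/or immediate temporization has been shown to compensate for tissue collapse.
- **Hypothesis (2.1).** Augmentation is expected to increase gingival thickness, and "stable gingival level and increased width of keratinized gingiva could also be found following soft tissue augmentation".
- **Grafts.** For the connective tissue graft, "The thickness of SCTG will be standardized as 1-1.5mm" (6.3 a). For the dermal matrix, "the thickness of ADM ranges from 0.9-1.6mm" (1.2 b). Both go into the buccal flap during first-visit surgery. All three arms receive xenograft in the gap (6.3 a).
- **Stent (6.3 b).** The first stent carries three buccal notches set 2 mm from the gingival margin. A second stent of the same design is made after the permanent restoration and used at 12 months. Item 1 records the notch-to-margin distance at baseline, 3, 6 and 12 months.
- **Status and analysis.** Sections 3.1 and 5.1 list change in gingival thickness as a secondary outcome, although 2.2 names it among the primary objectives. Section 11.2 c applies one-way ANOVA between arms and paired t-tests over time. It does not say which first-visit reading is the baseline.

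**The concern.** Items 4 and 8 both use a 6 mm level, but only item 8 ties it to the baseline margin. An examiner who follows item 4 as written would measure 6 mm from wherever the margin lies on the day. If the margin has receded, that point is further apical than the one read at the first visit, and the recorded change combines a change in thickness with a change of site.

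This matters for the comparison because the shift need not be equal across arms. If gingival level holds in the graft arms, as hypothesised, and recedes in the implant-alone arm, the ANOVA compares tissue at different heights. The error is systematic, so averaging over patients does not remove it.

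A smaller gap is that thickness has two first-visit readings, one on each side of graft insertion, and the plan does not say which one change is measured from.

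**Working it through.** The plan gives no expected change, SD or power for thickness, so it has no figure of its own to reproduce.

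**Inputs**

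- Nominal reading distance: 6 mm (item 4).
- Recession R: 0.5 to 1 mm within a year (1.1, background literature). R = 0 represents a stable level (the 2.1 hypothesis for the graft arms).
- Thickness gradient s along the buccal mucosa: not in the documents. Assumed 0 to 0.3 mm per mm, in either direction.
- Graft thickness g: 1 to 1.5 mm for connective tissue (6.3 a), 0.9 to 1.6 mm for dermal matrix (1.2 b).

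**Step 1: where the follow-up reading falls.** Distance from the baseline margin = 6 + R. With R = 0 it is 6 mm, with R = 0.5 it is 6.5 mm, and with R = 1 it is 7 mm.

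**Step 2: what this adds to the recorded change.** Apparent change = true change + s × R. The between-arm error is s × (R in implant alone − R in graft arm). With R = 0 in the graft arm:

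| Assumed gradient (mm per mm, either sign) | R = 0.5 mm | R = 1 mm |
|---|---|---|
| 0 | 0 | 0 |
| 0.1 | 0.05 mm | 0.10 mm |
| 0.2 | 0.10 mm | 0.20 mm |
| 0.3 | 0.15 mm | 0.30 mm |

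The error is proportional to the between-arm difference in recession. If that difference is half as large, so is the error, and if the arms recede equally it vanishes from the contrast. If tissue thickens apically, the implant-alone arm appears to gain and the benefit of grafting is understated. If it thins apically, the benefit is overstated.

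**Step 3: can this reverse a result?** For an illustrative graft-arm advantage of 0.5 mm, the worst cell gives 0.5 − 0.3 = 0.2 mm, still positive. A change near zero, as might occur within the implant-alone arm, could take the wrong sign.

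**Step 4: the two first-visit readings.** Let r be the share of the graft retained, hold native tissue constant, and assume the whole graft shows in the post-surgery reading. Change from the pre-surgery reading is g × r. Change from the post-surgery reading is g × r − g. The two differ by g whatever the value of r. For example, g = 1.0 mm and r = 0.5 give 1.0 × 0.5 = +0.5 mm from pre-surgery and 0.5 − 1.0 = −0.5 mm from post-surgery. The choice therefore matters, but the hypothesis in 2.1 is that augmentation increases thickness, and only the pre-surgery reading tests that.

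**The case against.** **The baseline margin may have been meant.** This is possible, since item 8 uses the same 6 mm level. If so, one added word settles item 4, but as it stands two examiners could read it differently.

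**Margin movement is already recorded.** Item 1 gives each patient's notch-to-margin distance, so the shift can be known. But nothing in the plan uses item 1 to locate the thickness point. At 12 months the notch is on a different stent, and nothing requires that notch to reproduce the first one's position.

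**The recession figure is background.** This stands. A reader might infer that the protocol expects 0.5 to 1 mm in its own control arm. Section 1.1 reports that figure for immediate implantation in general, and says grafting compensates for collapse. With xenograft in every arm, recession here may be smaller.

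**A reader might infer that recession could turn a thickness gain into a loss.** Step 3 does not support this for a gain of about 0.5 mm, even at the largest assumed gradient. The sign change in step 4 has a different cause: the choice of first-visit reading.

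**A reader might infer that the plan would use the post-surgery reading as baseline.** The documents do not say so, and it would conflict with 2.1. The before-and-after layout is also used for blood flow (item 12), which fits a description of the immediate surgical effect. The unnamed baseline is missing detail rather than an error.

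**A reader might infer from 2.2 that the primary analysis is at risk.** It is not. Sections 3.1 and 5.1 make thickness secondary, the ridge outcome is tied to the baseline margin, and the sample size does not rest on thickness.

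**Conclusion.** The point holds as an inexpensive improvement to a secondary outcome. Item 4 does not fix its reading site, and the recession cited in 1.1 together with the stable level hypothesised in 2.1 means the site could shift by different amounts in different arms. The resulting bias is zero with no thickness gradient, and about 0.05 to 0.3 mm if the gradient is 0.1 to 0.3 mm per mm and the implant-alone arm recedes 0.5 to 1 mm more than the graft arms. The gradient is an assumption, and the recession difference may be an upper case. A bias of this size could blur a small difference or a near-zero change, but would not reverse a gain of about 0.5 mm. The baseline for change needs only a clarifying sentence.

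**What to change.** 1. **Item 4:** state that every thickness reading, at the first visit, 6 months and 12 months, is taken mid-buccally at 6 mm from the *baseline* gingival margin, located with the notched stent. This matches the 6 mm level in item 8.
2. **Stent paragraph of 6.3 b:** require the new stent made after the permanent restoration to carry over the baseline margin position, for example from the baseline cast or scan, so that the 12-month reading uses the same point. Marking only the first stent would leave the 12-month reading unanchored.
3. **Sections 3.1 and 11.2 c (clarification only):** define change in thickness as the 6- or 12-month value minus the pre-surgery first-visit value. Report the post-surgery value descriptively, because in the graft arms it already contains the graft.

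The cost is protocol wording, some extra work to transfer the reference to the second stent, and a little time to seat the stent at each reading. No visit or measurement is added.
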